Building on the development of the SC-TF-CBT model,[4-7] this R01 application examines how to optimize the efficiency and cost-effectiveness of SC-TF-CBT, a personalized adaptive intervention, under “real world” settings. The proposed research is in line with NIMH research priorities for trials that foster personalized mental health care, incorporating tailoring variables to match interventions to patient needs, and to optimize interventions.[8] Consistent with RFA-MH-15-320, this application proposes to test a new service delivery approach compared to existing practice and to elucidate mechanisms of change within two-trauma focused interventions with the goal of improving the value and efficiency of trauma-focused treatment compared to standard practice. This project has the potential to improve the accessibility, efficiency, and effectiveness of clinical practice, while reducing the cost of treatment and reducing the societal impact of childhood PTSD.

**Aim 1:** To examine the relative efficacy of SC-TF-CBT (e.g., starting with Step One parent-led, therapist-assisted treatment and then either maintenance or Step Two TF-CBT) versus standard TF-CBT (e.g., therapist-led treatment).

**1.1. Hypothesis:** Given the second-stage treatments provided (maintenance, TF-CBT), children in SC-TF-CBT will demonstrate comparable improvements to children in standard TF-CBT in: (a) child outcomes: PTSD symptoms (PTSS) and functional impairment (primary outcomes), internalizing and externalizing behaviors, PTSD severity, and global improvement; (b) acceptability and satisfaction levels; and (c) parent secondary outcomes: parenting stress, depression, and PTSD symptoms.

**1.2. Hypothesis:** Children in SC-TF-CBT and standard TF-CBT will continue to have comparable improvements in child and parent outcomes throughout the 6- and 12-month follow-up period.

**Aim 2:** To examine tailoring variables that could be used to individualize (i.e., tailor) the decision of which children should be assigned at baseline to SC-TF-CBT versus standard TF-CBT.

**2.1. Hypothesis:** Children with high internalizing problems or high perceived critical life events are less likely to respond to first-stage Step One.

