**c.1.2. Candidate First-Stage Tailoring Variables.** An exploratory aim of the R34 was to explore differential characteristics of Step One responders/non-responders to identify potential first-stage tailoring variables. Based on prior literature and our clinical experience, we first explored differences in child variables (PTSD symptoms, internalizing and externalizing problems, depression, polytrauma (>1 traumatic event), interpersonal/non-interpersonal trauma, and age), parent variables (PTSD, depression and parenting stress) and environmental factors (treatment barriers) between Step One responders/non-responders. Two measures that showed substantial differences between responders and non-responders were internalizing problem T-scores and critical life events regarding barriers to treatment. We further applied classification tree method[78] to find the optimal cutoff values that maximally distinguished responder/non-responders after Step One. Regarding total internalizing T-scores, those children (16/49=32.7%) with a score >71 had a response rate of 56.3%, and those with a score ≤71 had a response rate of 87.9% ( $X^2=6.19$ ,  $p=.01$ ). Regarding critical life events, those children

(28%) with a score  $>16$  had a response rate of 44.4%, and those with a score  $\leq 16$  had a response rate of 82.6% ( $X^2=4.66, p=.03$ ). We recognize that given the small sample size, some of the results did not reach significance especially when adjusting for multiple comparisons. However, high internalizing problems is consistent with the literature suggesting that these children may need more intensive treatment [79, 80] and our qualitative findings are consistent with critical life event barriers as a theme for Step One non-responders. We considered externalizing problems as a first-stage tailoring variable since non-inferiority was not supported; however, there was not a significant difference between responders/non-responders and externalizing problems after Step One; nor was there a clear significant optimal cutoff value. Further, since GLM results and percentages of those above the clinical cutoff revealed no significant differences between SC-TF-CBT and TF-CBT at post- and follow-up, the evidence did not support externalizing problems as a tailoring variable. These results provide suggestive evidence of effect moderation and a preliminary establishment of candidate first-stage tailoring variables to be tested in the proposed application.

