### **c.3. Treatment Conditions INTERVENTIONS PROVIDED**

**c.3.1. Treatments.** Each treatment will be provided over 12-14 weeks, although flexibility will be allowed to minimize drop out. SC-TF-CBT patients will receive Step One: 3 (1 hr.) in-office therapist-led sessions over 6 weeks, the parent-child workbook (*Stepping Together*),[60, 61] scheduled weekly phone meetings (15 minutes), and information from the Stepping Together website and the National Center for Childhood Traumatic Stress website (via web or paper for those without access). Children who do not meet responder status will receive Step Two: 9 (1.5 hr.) in-office therapist-directed sessions of TF-CBT over 6 to 8 weeks. Standard TF-CBT patients will receive 12 (1.5 hr.) standard weekly in-office therapist-directed sessions (2 additional weeks allow for scheduling difficulty). TF-CBT includes child, parent and conjoint parent-child sessions addressing the 10 core trauma treatment components of TF-CBT (e.g., parenting skills, affect modulation, cognitive coping, trauma

narrative, etc.).[87] Is early termination of Step Two possible? For patients receiving step two TF-CBT, 9 sessions will be provided. However, in some cases, early termination may be possible. If two consecutive CGI-I parent and therapist ratings independently indicate a 2 (much improved), or 1 (free of symptoms) and the child is not in the middle of the trauma narration or conjoint component, the TSCYC-PTS total will be administered. If there is a 40 or less on the PTS total on the TSCYC measure, a post assessment with the IE may be scheduled. If responder status is met, the therapist will discuss with the parent the option of an early termination or continuing treatment. If treatment ends early, a final termination session may occur to discuss progress and relapse prevention. If the responder status is not met, the child will complete the step two treatment and there will be a post assessment upon completion.

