**c.3.2. Why use standard TF-CBT as the comparison condition?** The proposed study design allows for the direct comparison of Stepped Care TF-CBT, which is designed to increase efficiency, accessibility and cost effectiveness, to the traditional delivery of standard TF-CBT. TF-CBT has undergone RCTs comparing it to other active psychosocial treatments and waitlist controls. Another study demonstrating that trauma-focused components are superior to no treatment or to an inferior (and potentially non-credible) comparison does not challenge the current paradigm about how the field is delivering treatment (e.g., therapist-directed, “full treatment package” for everyone), nor does it allow for the comparison of value, efficiency, and non-inferiority relative to the current standard treatment. Within an adaptive treatment model that matches children to the appropriate level of care, some children will need standard TF-CBT and understanding mechanisms of change will allow clinicians to tailor treatment. Standard TF-CBT consists of 12 sessions [88] although some children may need less or more treatment.[26] When 8 vs. 16 TF-CBT sessions were tested, only 54% completed all 16 sessions, whereas 72% completed all 8 sessions [26] suggesting that barriers to treatment or perhaps early improvement led to dropping out. It is likely that children who respond in fewer sessions would also have the characteristics of the children who would respond to Step One. To optimize treatment in future practice, children who respond early to TF-CBT would be assigned to Step One first. Consistent with our pilot work, children may receive two additional sessions (see 5.1.1.a.) allowing some children to receive 14 sessions.

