## STUDY DESIGN AND SAMPLE SIZE

**c.4. Design/Randomization.** Participants (N=216, ages 4-12) are randomized and will receive SC-TF-CBT or TF-CBT in a 1:1 ratio within community-based agencies. To ensure the two treatment conditions are balanced in regard to candidate first-stage tailoring variables, a randomized block design will be used. Based on pilot results (see c.1.3.), we will divide our sample into four cells based on whether the child has internalizing T-scores > or ≤71 and whether s/he has a critical life events score > or ≤16. Each cell will have equal numbers of children assigned to SC-TF-CBT and TF-CBT. See “Other Attachment” for study timeline.

**c.4.1. Design Considerations. Why not conduct a Sequential Multiple Assignment Randomized Trial (SMART) to build the adaptive intervention?**[34, 89] **1)** The adaptive SC-TF-CBT has been developed [4-6] and is at the developmental stage of comparing it to the standard in the field (i.e., TF-CBT). Many of the questions that would have been examined in a SMART, such as effectiveness with different ages,[25, 90, 91] different types of traumas,[25, 63, 92] different components and different lengths,[26] and with and without medication[93] have consistently suggested that standard TF-CBT is the recommended treatment. **2)** Our pilot studies, designed to inform this R01 application, documented that a first-line parent-led approach is feasible and acceptable, identified an estimated number of Step One responders, demonstrated the clinical utility of the responder status criteria, and identified candidate first-stage tailoring variables and second stage time-varying tailoring variable. Thus, there is ample evidence for testing the confirmatory stage of an optimized adaptive intervention with a randomized clinical trial in community settings. **3)** In order to re-randomize after non-response there typically needs to be least 35% to 65% non-responders,[94] and our preliminary data after Step One indicate that 22% were non-responders. Once the first-stage tailoring variables are identified and children can be matched to appropriate treatment at baseline, we anticipate that the Step One non-response rate would be even less.

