## MEASURES

**c.6. Brief Description of Assessment Measures.** All patients will be asked to participate in assessments that will occur at screening/baseline, mid- post- treatment, and 6- and 12-month follow-up. Some data will be collected weekly (W). Demographic and web access information will be collected at screening (see Table 1).

**c.6.1. Measures Regarding the Child: Child PTSD:** Given empirical evidence for different manifestations of PTSD in children 6 and younger,[64, 65, 95] challenges of assessing PTSD directly with very young children, limited young child self-report measures,[96] and recommendations to include parent and child reports for older

Characteristics, outcome variables, tailoring variables	Timeframe			
	Screening baseline	Mid (week 6)	Post (week 13)	6 and 12 month follow-up
Demographics, EPF, SCID, TWQ, BIS	X			
DIPA; K-SADS*, TSCYC, UCLA PTSD Index, CSI-S, CSDS-P/C	X	X	X	X
CBCL, PCL-C, DASS, PSS, FASA, SDSC, RSS	X		X	X
CGI-I*		X	X	X
BTPS/*critical events	X		X	
CSQ			X	
Cost Measures				
CCI, SASA	X	X	X	X
TTTS	Every session/parent-child mtg. or activity			
Mechanisms of change				
CSDS-P, TSCYC (outcomes)	Every session and/or parent-child mtg.			
HR, SC. TASC (P, C, T)	Weeks, 0, 2,4 = Step One & 0,5,8= TF-CBT			
CPTCI	And at post-assessment			
SUD, ENOs, CFT	Every session and/or parent-child mtg. And at post assessment			

\* Trauma checklist section = every week in Step One. CGI-I = throughout treatment by therapists and caregivers. Critical events = baseline.

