**Primary Aim 2:** To examine tailoring variables that could be used to individualize the decision of which children should be assigned at baseline to SC-TF-CBT versus standard TF-CBT, we will compare the responders/non-responders of Step One with regard to the value of the tailoring variables. Based on results from pilot studies, we hypothesized that children with more internalizing problems at baseline and those from families with potential life event barriers are less suitable for SC-TF-CBT. A Chi Square test will be first applied to evaluate the association between the dichotomized candidate tailoring variable and responding status. Next, we will use GLM, in which responding status will be treated as the dependent variable and tailoring variables as continuous predictors. To further quantify the relation between the value of the tailoring variables and the propensity of not responding to Step One, we will include in the GLM the products of the tailoring variables to evaluate their interactions. Demographics will also be controlled in the model. While it was not a primary aim, we will further explore whether race/ethnicity or gender moderate the dropout rate and treatment outcomes (see 6.). This will be done in a separate analysis where interactions with treatment condition are included.

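### Aim 2 asks which treatment suits which child, but its tests use Step One response in the SC-TF-CBT arm only and cannot show differential benefit

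*Combined protocol and SAP*

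**What the plan says.** The Specific Aims and section c.8.3 both put Aim 2 as a choice between two treatments: "which children should be assigned at baseline to SC-TF-CBT versus standard TF-CBT". Hypothesis 2.1 is narrower. It says that children with high internalizing or high critical-events scores "are less likely to respond to first-stage Step One".

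The tests follow the hypothesis. Section c.8.3 states "we will compare the responders/non-responders of Step One with regard to the value of the tailoring variables", first by chi-square on the dichotomised variables and then by a GLM of responder status on the continuous scores. The only products in that GLM are of one tailoring variable with the other. Interactions with treatment condition are planned for race/ethnicity and gender only. Section c.9 bases Aim 2 power on 92 children, all in the SC-TF-CBT arm. The 2022 amendment changes Aim 2 to backward stepwise logistic regression with a p<.01 criterion and states no treatment-by-tailoring-variable term.

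The design would support such a term. Randomisation is blocked on these two variables, and section c.4 says "Each cell will have equal numbers of children assigned to SC-TF-CBT and TF-CBT". Section c.6 puts both arms on one outcome schedule: "All patients will be asked to participate in assessments that will occur at screening/baseline" and at the later time points, with TSCYC and CSDS-P at each of them (Table 1).

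**The concern.** Recommending one treatment over another for high scorers requires knowing how high scorers do under both. A comparison inside the SC-TF-CBT arm does not supply this, for two reasons.

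- **Prognosis and moderation are confounded.** A score that predicts poor response whatever the treatment gives the same significant result as a score that identifies children better served by standard TF-CBT. Section c.3.2 gives some reason to expect overlap: "It is likely that children who respond in fewer sessions would also have the characteristics of the children who would respond to Step One".
- **Step One response is an intermediate outcome.** Section c.3.1 states "Children who do not meet responder status will receive Step Two". A child can fail Step One and still finish as well as under standard TF-CBT.

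The risk of over-reading is visible in the text. Section c.1.2 compares Step One responders with non-responders and concludes "These results provide suggestive evidence of effect moderation". Section c.8.3 moves from the same pilot data to lower suitability for SC-TF-CBT. Under Aim 4 it then treats standard TF-CBT as needed for high scorers and leaves them out of the subgroup cost-effectiveness analysis. A significant Aim 2 result could be read in the same way.

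**Working it through.** **1. The plan's own figure.** Section c.9 claims 80% power for 62% vs 30%, 72% vs 40% and 80% vs 50%, with 46 children per group. No alpha is given for Aim 2.

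Power = Φ{[d − z·SE0]/SE1}, where SE0 uses the pooled rate and SE1 the separate rates. For 62% vs 30%:
- SE0 = √(2 × .46 × .54/46) = .1039
- SE1 = √[(.62 × .38 + .30 × .70)/46] = .0984
- at two-sided .05: (.32 − 1.96 × .1039)/.0984 = 1.18, power 88.1%.

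The other two pairs give 88.4% and 86.7%. At two-sided .025 (.05 split over two variables, my assumption) the three are 81.2%, 81.6% and 79.3%. The 80% figure is therefore attainable and is not the problem.

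**2. What the one-arm test does when there is no differential benefit.** Assume both arms share the pilot internalizing rates in c.1.2: 87.9% at or below the cutoff, 56.3% above it, with 16/49 = 32.7% above. Group sizes, low/high:
- 61/30: the 91 children randomised to SC-TF-CBT
- 44/22: 183 × (1 − .2787) = 132, halved to 66 per arm. This assumes equal attrition by arm and stratum and applies the amendment's overall figure to Step One.

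For 61/30, the pooled rate is .775, SE0 = .0932, SE1 = .0997 and d = .316:
- alpha .05: (.316 − 1.96 × .0932)/.0997 = 1.34, giving .910
- alpha .01: (.316 − 2.576 × .0932)/.0997 = 0.76, giving .777.

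| Shared rates, low vs high | .05: 61/30, 44/22 | .01: 61/30, 44/22 |
|---|---|---|
| 87.9 vs 56.3 (full gap) | .910, .809 | .777, .616 |
| 87.9 vs 72.1 (half gap) | .468, .370 | .259, .184 |
| 82.7 vs 66.9 (half gap, overall 77.6% held) | .402, .315 | .203, .143 |

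Simulation of the full gap at .01 gave .794/.645 (Pearson), .778/.622 (likelihood ratio) and .771/.582 (Wald), so the choice of test widens 62-78% to about 58-79%. These are univariate approximations, and the amendment does not say whether .01 governs entry or retention.

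**3. The treatment-by-score test in the same full-gap scenario.** With a like-for-like response endpoint in both arms at .05, the rejection rate is .044/.038 (logit Wald) or .057/.061 (risk-difference Wald). Using section c.9's own rate pairs with 46 per cell, the one-arm test rejects in 87-88% of simulated trials and the interaction test in about 5%.

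**4. Precision of the missing analysis.** Unit SD, 66 or 91.5 children per arm, 32.7% high; with an assumed baseline correlation r, each SE is multiplied by √(1 − r²). The dichotomised interaction has SE = √(2/nh + 2/nl), where nh and nl are the high and low counts per arm. The continuous interaction has SE = 2/√N.

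| Quantity (66, 91.5 per arm) | r = 0 | r = .6 | r = .7 |
|---|---|---|---|
| SE, dichotomised | .371, .315 | .297, .252 | .265, .225 |
| SD detectable at 80% power (2.80 × SE) | 1.04, .88 | .83, .71 | .74, .63 |
| Power for 0.41 SD | .20, .26 | .28, .37 | .34, .45 |
| Continuous: SD per 1 SD of score, 80% power | .49, .41 | .39, .33 | .35, .30 |
| 95% half-width, arm difference in high stratum | .60, .51 | .48, .41 | .43, .36 |

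**The case against.** The strongest reply is that the plan's purpose is efficiency. The project summary and section b.3 speak of matching the starting intensity to the child. Since Step One non-responders go on to therapist-led sessions, predicting non-response is directly useful for choosing the entry point. The tests also match Hypothesis 2.1 as worded. Both points stand, and the Step One regression is valid for that use. They do not extend to a claim that high scorers do better on standard TF-CBT, which the Aim 2 wording and sections c.1.2 and c.8.3 suggest.

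Other points have weight:
- Section c.3.2 concerns speed of response, so it supports a shared prognosis only indirectly.
- Section c.1.2 calls its evidence preliminary and admits the small sample. Its cutoffs were chosen to separate responders best among 49 children, so the full gap is probably optimistic; the half-gap rows address this.
- Between-arm analyses by score were planned under Aim 4: a conditional cost-effectiveness analysis in low scorers, and power for cost differences in low and high scorers. They are mainly economic, and the amendment replaced the cost-effectiveness analysis with a cost comparison. They do not fill the gap.
- The amendment is brief and does not specify the Aim 2 population, so its silence does not prove that no interaction was fitted. None is stated, however.
- The interaction would be post hoc and weakly powered. That limits what it can show but does not make the one-arm test answer the comparative question.

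**Conclusion.** The concern holds. Aim 2 poses a between-treatment question, and its stated tests and power use one arm and an intermediate outcome. A significant result would support a statement about who responds to Step One and nothing about how the same children fare under standard TF-CBT. The logic does not depend on any figure. The size is illustrative: with a purely prognostic score carrying the full pilot gap, the one-arm test is significant in about 81-91% of trials at .05 and 62-78% at .01. With half the gap the ranges are 31-47% and 14-26%, depending on which rate is held. These figures assume rates shared by both arms, the pilot's 32.7% high scorers, and 66 to 91 children in the SC-TF-CBT arm. This should be fixed, because it determines what a primary aim may conclude.

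**What to change.** 1. **Minimum.** Present the Step One regression as prediction of Step One response, useful for efficiency triage, and draw no differential-benefit assignment rule from it. Alternatively, restate Aim 2 to match Hypothesis 2.1. This is a change of wording only.
2. **Addition.** In the Aim 1 mixed model, with both arms and baseline adjustment, add treatment-by-internalizing T-score and treatment-by-critical-events terms (continuous scores) for TSCYC-PTS and CSDS-P. Report the SC-TF-CBT minus standard TF-CBT difference with its confidence interval in each randomisation stratum.

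The addition costs a few model terms on outcomes scheduled in both arms. The amendment describes completed analyses, so the terms must be labelled post hoc and exploratory. They will be imprecise: even with the assumed baseline adjustment, power for a dichotomised 0.41 SD interaction is 28-45%. The interval half-width for all high-internalizing children is 0.51-0.60 SD unadjusted, or 0.36-0.48 SD adjusted, against a margin of 0.41; intervals in the four smaller randomisation cells will generally be wider. The results should be reported as estimates with intervals, not as a decisive test.
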